## **3. Abstract**

Chronic poor sleep is prevalent among college students and has wide-ranging negative consequences, including poorer academic performance, increased health risk behaviors, and greater risk for mental health problems. Despite this fact, estimates suggest that 80-90% of students with chronically poor sleep are not receiving help from their college or university. Likewise, college student mental health, which shares a bidirectional relationship with sleep quality, has become a significant and growing public health concern. Estimates suggest that roughly one third of college students meet criteria for a clinically significant mental health problem, and rates of depression, anxiety, and suicidality are rising. Digital mental health programs, delivered via mobile app, present one promising approach to address this need and expand treatment accessibility. In particular, mindfulness mobile apps have achieved both mental health and sleep benefits across several randomized controlled trials in student populations; however, adherence and sustained use after interventions have been low. Thus, it is important to address barriers to sustained mindfulness practice in order to optimize user outcomes.

The current study explores using tVNS as a potential method to alleviate barriers to establishing a habit of mindfulness practice. In mindfulness interventions it is not uncommon for participants to report an initial escalation of anxiety and distress as they directly engage with negative thoughts. While accepting, decentering, and deriving meaning from these negative reactions is an important feature of the psychotherapeutic process in mindfulness interventions, they can also lead to disengagement or drop out from the intervention. Similarly, difficulty learning the skill of meditation is also common and can contribute to participant dropout. tVNS may exert an anxiolytic effect through effects on limbic structures and activation of the parasympathetic nervous system. Moreover, tVNS increases positive affect (i.e. calm) and has been linked to improved interoceptive awareness, which are two other potential psychological mediators of mindfulness interventions. Thus, these two separate treatment approaches appear complementary, yet there are no published trials using them in combination. **The proposed study will enable us to evaluate the utility of this combined treatment approach in enhancing college student sleep and mental health, with potentially broader impacts for clinical populations.**

## **4. Background**

Insufficient sleep in the United States has recently been recognized as a public health epidemic. College students are at increased risk of experiencing poor sleep due to a “perfect storm” of challenging biological, social, and environmental factors, including delayed circadian rhythm, early class times, residential sleep environments, high stress levels, increased social demands, and greater substance and electronic use. Chronic poor sleep is prevalent among college students;

more than one third have identified sleep difficulties as “traumatic or very difficult to handle.” Despite the prevalence and increasingly well-known negative consequences of poor sleep, sleep health has not historically been prioritized as an area for intervention on college campuses. For instance, according to the 2018 Center for Collegiate Mental Health annual report, approximately 11,000 students reported sleep disturbances on intake, yet less than one percent had that concern prioritized by clinicians. Moreover, when sleep questions were included as part of a universal behavioral health screening survey, more than 10% of students requested support for their sleep concerns. Thus, there is a clear unmet need for sleep intervention among college students.

Importantly, sleep and mental health share a bidirectional relationship, and the prevalence of sleep problems on college campuses parallels the high rates of anxiety and depressive symptoms. In large national studies, approximately 41% of United States college students report moderate to severe depressive symptoms and 34% report moderate to severe anxiety symptoms. These mental health problems are associated with a variety of negative outcomes, including greater substance use, poorer academic performance, increased self-harm behaviors, and suicidal ideation and attempts. While counseling centers can be found on most college campuses, the increased demand for mental health services has unfortunately not been met with a proportional increase in counseling center staff and funding. As a result, many counseling centers are under-resourced and operate at full capacity with waitlists for much of the year. On a nation-wide survey of college counseling center directors, 90% raised concerns that students may not be receiving treatment when it is most needed. As a result, there is growing interest in digital mental health interventions, such as mindfulness apps, to expand treatment accessibility and improve student well-being and sleep quality.

Though digital mindfulness interventions offer many potential sleep and mental health benefits for college students, rates of adherence and sustained use of mindfulness apps have been low. Thus, more research needs to examine facilitators to the uptake and sustainability of mindfulness practice, as well as complementary treatment methods that can boost the perceived effectiveness of mindfulness practice. The current study explores tVNS as one such complementary treatment. tVNS is a safe, non-invasive form of vagus nerve stimulation (FDA-approved for the treatment resistant depression and epilepsy). tVNS targets the auricular branch of the vagus nerve through stimulation at sites of the external ear, such as the inner tragus. It has been shown to affect vagally mediated components of the limbic system that are critical to sleep and mood via activation of the nucleus of the solitary tract (NTS). Moreover, tVNS has been shown to increase parasympathetic tone, which can have a beneficial effect on both sleep and mood. Stimulation of the vagus nerve has been associated with reductions in daytime sleepiness, decreased sleep latency, greater slow wave sleep, and longitudinal improvements in self-reported sleep quality in clinical and preclinical studies. tVNS has also been associated with improvements in anxiety and depressive symptoms. Thus, tVNS may be a convenient means to improve sleep and mental health outcomes among college students engaging in mindfulness practice, although this potential has not yet been empirically tested. The current study will evaluate the feasibility, acceptability, and efficacy of this novel combined treatment approach relative to mindfulness-only and control conditions.

## 5. Specific Aims

The goal of the proposed research project is to explore the acceptability and efficacy of a combined transcutaneous vagus nerve simulation (tVNS) and mindfulness intervention in enhancing sleep and well-being among college students and compare it to mindfulness-only and control conditions with the hypothesis that the combined intervention will have greater efficacy due to synergistic brain effects of tVNS and mindfulness. In addition to experimental results, the proposed project will

generate effect size data to inform future trials of the combined approach and assess the feasibility and acceptability of our study design.

**Specific Aim 1:** To evaluate the feasibility and acceptability of sustained engagement with the Brightmind mindfulness app among college students.

Research question 1.1: Do students find this app acceptable and engage with it consistently across a 4-week period?

Research question 1.2: What are the barriers and facilitators to sustained engagement with the app?

Hypothesis 1.3: Participants who spend more time engaging with the app will see greater improvements in mental health (e.g., stress, anxiety, depressive symptoms, positive affect) and HRV compared to participants who spend less time engaging with the app.

**Specific Aim 2:** To obtain preliminary effect size data on the efficacy of the Brightmind mindfulness app in improving proximal and distal mental health outcomes among college students

Hypothesis 2.1: Participants in the mindfulness-only group will demonstrate greater improvements in mental health (e.g., stress, anxiety, depressive symptoms, positive affect) than participants in the control group

Hypothesis 2.2: Overnight heart rate variability (HRV), positive affect, and interoceptive awareness will be greater in the mindfulness-only group compared to the control group.

Hypothesis 2.3: HRV will increase from before to after each mindfulness session.

**Specific Aim 3:** Determine feasibility and acceptability of the combined tVNS + mindfulness intervention.

Research question 3.1: Do students find this combined intervention acceptable and demonstrate adequate adherence (i.e. use tVNS or sham + mindfulness for at least 10 minutes/day at least 4 days/week for 2 weeks)?

Research question 3.2: What are the barriers and facilitators to adherence with the combined intervention?

Hypothesis 3.3: The combined intervention will be well-tolerated and receive positive acceptability ratings.

**Specific Aim 4:** Develop effect size data on the efficacy of the combined tVNS + mindfulness intervention in improving sleep and mental health among college students.

Hypothesis 4.1: Participants in the tVNS + mindfulness group will demonstrate greater improvements in sleep quality and quantity than participants in the sham + mindfulness group or control groups.

Hypothesis 4.2: Participants in the tVNS + mindfulness group will demonstrate greater improvements in mood and mood related factors ( e.g., stress, anxiety, depressive symptoms, positive affect) than participants in the sham + mindfulness group or control groups.

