## 6. Research Plan

**6.1 Study timetable and logistics.** The study will consist of an intake-training session and a 4-week intervention phase. Participants will complete brief weekly online surveys during the intervention phase and a follow-up online survey 4-weeks after the end of the intervention period. Face-to-face interaction with subjects will take place at the University of Florida McKnight Brain Institute (MBI) during the intake-training visit, the return of study equipment, and the distribution of participant payment

**Figure 1** Visualization of the study protocol and timeline.

**6.2 Experimental design.** As participants are scheduled for intake visits, they will be assigned to either a tVNS group (tVNS + mindfulness or sham + mindfulness) or a non-tVNS group (mindfulness only or control) by the research coordinator based on practical considerations (i.e. tVNS device availability) to expedite study completion. Within each of these groups, participants will be randomized via alternating order to either the active or control condition (in other words, once a participant is assigned to a tVNS group, they will then be randomized to either the tVNS + mindfulness or sham + mindfulness group). This process will repeat until each group has the target number of participants.

In the initial visit, a research assistant will review the appropriate informed consent form. During this process, participants assigned to a stimulation group (tVNS + mindfulness or sham + mindfulness) will be told that they have been randomized to receive one of two different types of noninvasive vagal nerve stimulation, that we think one of the conditions may be more effective, and that they have a 50/50 chance of being in that group. For participants randomized to the non-stimulation groups (mindfulness only or control), they will be told that they have been randomly assigned to use one of two mobile app interventions, that we think one of the interventions may be more effective, and that they have a 50/50 chance of being in that group. After providing written informed consent, participants will complete a brief health questionnaire as part of our inclusion/exclusion screening (see section 6.5). If participants screen out after signing the informed consent, the session will end, and any data collected will be kept in a locked filing cabinet.

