After passing the screening, participants will complete an online survey that will include measures of mood, well-being, pain, daytime sleepiness, and sleep quality (see section 6.6 for specific measures).

These measures are self-report and will establish a baseline for each participant. They will be provided with and trained on the following equipment depending on their group assignment:

- **Brightmind Meditation mobile mindfulness app** (Brightmind Meditation, LLC; <https://www.brightmind.com>): Participants in each of the three active treatment groups (tVNS + mindfulness, sham + mindfulness, and mindfulness-only) will be provided with free access to the Brightmind mobile mindfulness app. During the intake session, they will download the app and complete an orientation to learn its features. They will be asked to practice mindfulness meditation through the app for 10 minutes each evening during the 4-week

intervention phase, with compliance defined as using the app 10 minutes/day for at least 4 days/week.

- **Control task:** Participants in the control group will be provided with the link and instructions for a control task (an online number puzzle: <https://play2048.co/>) that has been used in previous studies of mindfulness apps. They will be asked to engage with this control task for 10 minutes each evening during the 4-week intervention phase, with compliance defined as engaging with the task 10 minutes/day for at least 4 days/week. Participants in the control group will receive free access to the Brightmind mindfulness app after study completion.

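### The overall goal credits synergy, which these four arms cannot isolate, and names comparators that lie across a non-random allocation step from the combination

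*Combined protocol and SAP*

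**What the plan says.** The overall goal in 5. Specific Aims is to study the combination and to "compare it to mindfulness-only and control conditions with the hypothesis that the combined intervention will have greater efficacy due to synergistic brain effects" of its two components. 4. Background promises the same comparison, the "efficacy of this novel combined treatment approach relative to mindfulness-only and control conditions". Neither sentence mentions the sham arm.

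Hypothesis 4.1 is worded differently: the combination should show "greater improvements in sleep quality and quantity than participants in the sham + mindfulness group or control groups". Hypothesis 4.2 ends the same way for mood. The closing plural is not defined, although Table 1 calls only one arm control.

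Section 6.2 gives the app to "Participants in each of the three active treatment groups (tVNS + mindfulness, sham + mindfulness, and mindfulness-only"). The fourth arm does a number puzzle. Table 1 lists 20 participants in each of the four arms.

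Allocation has two steps (section 6.2). People are first placed in the stimulation pair or the non-stimulation pair "by the research coordinator based on practical considerations (i.e. tVNS device availability) to expedite study completion". Within a pair, "participants will be randomized via alternating order to either the active or control condition".

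The Analysis Plan, under section 6.6, enters group as a moderator of linear and quadratic time trends. It names no contrast between arms and does not address the coordinator-assigned step.

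**The concern.** Synergy means that two treatments together do more than the sum of their separate effects. To see it, one needs to know what each does alone. Mindfulness alone can be compared with the control task, but there is no arm for tVNS alone.

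The comparators raise a second difficulty. Mindfulness-only and control are both in the other pair from the combination, so each comparison in the overall goal crosses the step that the coordinator decides. The pairs also differ in more than stimulation. They hear different consent explanations (section 6.2), pregnancy tests are given only in the stimulation groups (6.3), and removal at calibration can happen only there (6.6, Calibration).

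The project is meant to supply effect sizes for later trials. An effect size taken across the pairs would carry selection and device ritual into that planning. An effect labelled as synergy could lead a later trial to assume an interaction that this one never measured.

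**Working it through.** **Arms.** Table 1 gives 4 × 20 = 80, which agrees with the 80 in section 6.3. The documents give no power calculation to reproduce.

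**Arm means.** Let μ be the mean under the control task, M the mindfulness effect relative to that task, T the effect of active tVNS, and TM its interaction with mindfulness (the synergy). Let R be device ritual and expectancy, and S the effect of who is assigned to the stimulation pair, and when.

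| Arm | Mean |
|---|---|
| A: tVNS + mindfulness | μ + M + T + TM + R + S |
| B: sham + mindfulness | μ + M + R + S |
| C: mindfulness only | μ + M |
| D: control | μ |

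**Contrasts.**

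- A − B = T + TM. R and S cancel because both arms go through them; for R this assumes that blinding holds.
- A − C = T + TM + R + S (comparator in the overall goal).
- A − D = M + T + TM + R + S (comparator in the overall goal and in 4.1/4.2).
- C − D = M (Aim 2; does not cross the pairs).
- B − C = R + S, so ritual and selection cannot be told apart either.

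**Estimability.** T and TM both appear in arm A and nowhere else, so their columns in the arm-level design matrix are identical. With columns for the intercept, M, T and TM the rank is 3 out of 4. Adding one column for the stimulation pair (R + S together) gives rank 4 out of 5. In both cases M and the sum T + TM are estimable, while T alone and TM alone are not.

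**Illustration (assumed figure).** Suppose A − B = 0.5 SD. That fits T = 0.5 with TM = 0, or T = 0 with TM = 0.5. It also fits T = 0.8 with TM = −0.3, or T = −0.2 with TM = 0.7. The split has no bounds.

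**Would a tVNS-only arm solve it?** Call that arm E, placed in the stimulation pair, with mean μ + T + R + S. Then A − E − C + D = (M + TM) − M = TM, provided that the pair effect is additive. The rank rises to 4 out of 4, or 5 out of 5 with the pair column. The documents give no alpha, power or SD, so I assume two-sided 0.05, 80% power, 20 per arm, SD = 1 and no dropout:

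- Pairwise contrast: SE = √(2/20) = 0.316; detectable difference = (1.960 + 0.842) × 0.316 = 0.89 SD.
- Interaction: SE = √(4/20) = 0.447; detectable difference = (1.960 + 0.842) × 0.447 = 1.25 SD.

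If repeated measures cut the residual SD to 0.7, these become 0.7 × 0.89 = 0.62 and 0.7 × 1.25 = 0.88. The interaction SE is √2 times the pairwise SE in either case, so an added arm would give only an imprecise estimate of synergy.

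**Comparators side by side.**

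| Comparator | Overall goal and Background | 4.1 and 4.2 | Same pair as the combination? |
|---|---|---|---|
| Sham + mindfulness | not named | named | yes, by alternation |
| Mindfulness only | named | not named; possibly covered by the plural | no |
| Control | named | named | no |

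**The case against.** The strongest reply is that synergy is a reason for expecting benefit and not something the trial sets out to estimate. It stands in one explanatory clause. None of the numbered research questions or hypotheses tests it, and Aim 4 seeks effect sizes. This stands: the missing arm defeats no planned analysis. A reader might infer that the sponsor plans to report synergy, or that the trial cannot assess the combination at all. The documents support neither, since T + TM can be estimated.

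A reader might also infer that the goal and the hypotheses contradict each other. They overlap on control, and the undefined plural could take in mindfulness-only. The clear difference is that 4.1 and 4.2 name sham and the goal does not. What is needed is a definition.

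It is also tempting to treat the comparators in the goal as the unsound ones and those in 4.1 and 4.2 as randomised. That does not hold either. The control comparison in the hypotheses crosses the same coordinator step, and the split between active and sham is by alternating order, which is predictable.

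Two further replies carry some weight. Section 6.2 gives device availability, not participant characteristics, as the basis for assignment, so bias is possible but not shown. And although no direct brain measure is listed, positive affect, interoceptive awareness and HRV are measured. They bear on mechanism, but they cannot separate synergy from an additive effect, because the missing piece is an arm and not an outcome.

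**Conclusion.** The point holds as one about what may be concluded. The attribution to synergy cannot be examined with these four arms at any sample size; this follows from the list of arms and needs no assumed figure. The contrasts with mindfulness-only and control mix the treatment effect with selection, device ritual and expectancy by an amount that the documents do not allow one to compute, and the analysis model does not address this.

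Active versus sham is the best protected efficacy contrast for the combination. It estimates the effect of tVNS when given with mindfulness, on two conditions: that blinding keeps ritual and expectancy equal in the two arms, and that alternation has not let anyone steer allocation. Mindfulness-only versus control is untouched by the missing arm and by the coordinator step, though it too is allocated by alternation. Given the exploratory purpose, this is a worthwhile correction of claims and labels, not a fault that undermines the study.

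**What to change.** - In 5. Specific Aims and the Analysis Plan, name tVNS + mindfulness versus sham + mindfulness as the main efficacy contrast, described as the added effect of tVNS when given with mindfulness. Bring the matching sentence in 4. Background into line.
- Remove the clause on synergistic brain effects, or mark it as rationale that this trial does not test.
- Define the control groups in Hypotheses 4.1 and 4.2, so that the goal and the hypotheses name the same comparators.
- State that every contrast across the two pairs is non-randomised and will be reported descriptively, including the control comparison within 4.1 and 4.2.
- In section 6.2, describe the within-pair allocation as alternation and not as randomisation.

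No arm, participant or procedure is added. The cost is a narrower claim. Rewording does not repair the allocation itself; it only keeps the conclusions within what the allocation supports. I would not ask for a tVNS-only arm, given how imprecise the interaction estimate would be at about 20 per arm.

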- **Soterix Medical RELifit-Tragus Device** (Soterix Medical Inc.; <https://soterixmedical.com/research/tavns>): Participants in the tVNS + mindfulness and sham + mindfulness groups will be provided with the Soterix Medical RELifit-Tragus device, as well as its accompanying equipment (e.g., device charger, gel, cleaning materials). During the intake session, they will be trained on procedures for using the device, including gel application, electrode placement, and device configuration. Once the research assistant confirms that the participant understands how to apply the electrodes and set the stimulator, the research assistant will demonstrate how to take a picture of the electrode application to check the quality of the application. Participants will be instructed to take a picture that hides the identifying features of the face. Participants will be asked to administer tVNS concurrently with mindfulness practice for at least 4 days per week for the first 2 weeks of the intervention phase. They will be asked to send a picture of the application of the electrodes for each stimulation session. If a picture of the application indicates improper placement, a research assistant will contact the participant via phone or email to review proper form.
- **Fitbit Wristband** (Fitbit LLC): All participants will be provided with a Fitbit wristband for overnight sleep and HRV measurement. They will be instructed on the best method for wearing the band during the initial visit. Participants will be asked to wear the wristband overnight each night for the 4-week intervention phase, with compliance defined as wearing the device overnight at least 4 nights/week.
- **Polar H10 Chest Strap** (Polar Electro; [https://www.polar.com/us-en/products/accessories/h10\\_heart\\_rate\\_sensor](https://www.polar.com/us-en/products/accessories/h10_heart_rate_sensor)): All participants will be provided with a Polar H10 chest strap for HRV measurement during mindfulness practice. They will be instructed on the best method for wearing the chest strap during the initial visit. In addition, the research assistant will assist them in downloading a mobile app for data collection/storage and pairing it with the Polar H10 band for HRV recording. They will be asked to wear the chest strap during at least one mindfulness practice session per week during the 4-week intervention period.

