After receiving study equipment and completing training procedures, participants will begin the intervention phase at home. They will be provided with written and/or video instructions as a reminder of procedures for the intervention phase depending on their group (summarized in **Table 1**). Study staff will also be available to answer questions or provide reminders via email and/or phone. During the intervention phase, participants will complete brief weekly online surveys consisting of some of the measures administered at baseline (see section 6.6). The survey will be sent via an electronic link to participants' email address or phone number. At the completion of the 4-week intervention phase, the research assistant will coordinate with the participant to schedule a time to return study equipment and distribute participant payment. Participants will be compensated for their time and effort (see section 10).

Group	Intervention Phase Procedures
-------	-------------------------------

tVNS + mindfulness (n = 20)	
 
- Practice mindfulness meditation through the Brightmind Meditation app for 10 minutes each evening for 4 weeks
 
- Administer tVNS concurrently with mindfulness practice at least 4 days per week during the first 2 weeks of the intervention phase
 
- Wear the Polar H10 chest strap during mindfulness practice at least 1x/week
 
- Wear the Fitbit overnight for 4 weeks
 

Sham + mindfulness (n = 20)	
 
- Practice mindfulness meditation through the Brightmind Meditation app for 10 minutes each evening for 4 weeks
 
- Administer sham stimulation concurrently with mindfulness practice at least 4 days per week during the first 2 weeks of the intervention phase
 
- Wear the Polar H10 chest strap during mindfulness practice at least 1x/week
 
- Wear the Fitbit overnight for 4 weeks
 

Mindfulness only (n = 20)	
 
- Practice mindfulness meditation through the Brightmind Meditation app for 10 minutes each evening for 4 weeks
 
- Wear the Polar H10 chest strap during mindfulness practice at least 1x/week
 
- Wear the Fitbit overnight for 4 weeks
 

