Control (n = 20)	
 
- Engage with the control task for 10 minutes each evening for 4 weeks
 
- Wear the Polar H10 chest strap during the control task at least 1x/week
 
- Wear the Fitbit overnight for 4 weeks
 

**Table 1.** Intervention phase procedures for each experimental group.

**6.3 Subjects.** This study utilizes a between-participant design and will recruit 80 healthy college students aged 18 – 30. Pregnant women may not participate in this study—pregnancy tests provided by the study will be used for women of child-bearing age randomized to a tVNS group prior to starting the study and after the consenting process. Pregnancy tests will only be given in the intake session.

**6.4 Recruitment and Retention.** We will recruit a volunteer sample of undergraduate students from the Gainesville, Florida community who are interested in managing stress. We will post IRB-approved flyers around the community and on the UF campus. The flyers include a survey link where interested students can provide their contact information if they believe they qualify for the study to allow study staff to contact them to schedule an intake appointment. The investigators will be involved in recruitment of participants from multiple sources, including campus tabling events, posting flyers on UF campus and through GatorWell, emails to relevant listservs, making announcements during undergraduate classes, and through word of mouth. The investigators will also post announcements to Facebook and Twitter (see Social Media Strategy). Subjects will be expected to provide their own means of transportation.

**6.5 Inclusion/Exclusion Criteria.** Participants will include adults between the ages of 18-30, consistent with the typical college population. Participants must own a smartphone, be able to read and write English, and not be in ongoing psychotherapy.

Major medical illnesses including diagnosed severe neurological illnesses (e.g., stroke, seizure history), medical conditions associated with neurological effects (e.g. heart, kidney disease), autoimmune disorders, and severe psychiatric diseases (e.g., schizophrenia) will be excluded. Participants with any history of brain surgery, tumor, intracranial metal implantation, pacemakers or other implanted devices will be excluded. These elements will be assessed via self-report.

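### Hypothesis 2.3 is a before-after statement on session HRV with no comparator, placed under the app-efficacy aim, although the control arm is scheduled to wear the same strap during its own 10-minute task

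*Combined protocol and SAP*

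**What the plan says.** Aim 2 in section 5 is "To obtain preliminary effect size data on the efficacy of the Brightmind mindfulness app". Three hypotheses follow. H2.1 compares mindfulness-only with control on mental health. H2.2 does the same for overnight HRV, positive affect and body awareness: "interoceptive awareness will be greater in the mindfulness-only group compared to the control group". H2.3 says "HRV will increase from before to after each mindfulness session" and names neither a control group nor the arms whose sessions count.

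Section 6.2 says: "All participants will be provided with a Polar H10 chest strap for HRV measurement during mindfulness practice". Table 1 extends this to the control arm: "Wear the Polar H10 chest strap during the control task at least 1x/week". The two schedules match in length and timing: "Practice mindfulness meditation through the Brightmind Meditation app for 10 minutes each evening for 4 weeks" for the mindfulness arms, and "Engage with the control task for 10 minutes each evening for 4 weeks" for control. The strap is required in at least one session a week, and the participant may choose which. In the active stimulation arm, Table 1 adds: "Administer tVNS concurrently with mindfulness practice at least 4 days per week during the first 2 weeks of the intervention phase". The sham arm has the same schedule.

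The Analysis Plan in section 6.6 uses multilevel models with group as a moderator of time trends in sleep and mental health or well-being measures. It does not mention session HRV and describes no within-session contrast.

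**The concern.** A change from before to after in one arm mixes the effect of the app with everything else that happens in those ten minutes: sitting still, settling after putting on the strap, the time of evening. H2.3 is the only hypothesis under Aim 2 without a control comparison, and H2.2 does not fill the gap because it concerns overnight HRV from a different device. Section 5 says the project's effect sizes are to inform future trials, so an uncontrolled change could be carried forward as an app effect.

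The arms are also left open. Three arms use the app. In weeks 1 and 2 a recorded session in a stimulation arm may or may not include stimulation, because app use is asked for every evening and stimulation on at least four days a week. Section 4 itself says that tVNS raises parasympathetic tone. Including such sessions could therefore put a stimulation effect into an estimate meant for the app.

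**Working it through.** **The plan's own figure.** There is none to reproduce. The documents give no alpha, power, effect size, SD or dropout rate for this outcome, and no test of within-session HRV.

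**Inputs from the documents.** Mindfulness-only n = 20 and control n = 20 (Table 1); at least one strap recording a week for 4 weeks, so 4 sessions per person at the minimum.

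**Assumptions, not from the documents.** Non-specific rise r of 0.05, 0.10 or 0.15 in log HRV; session SD 0.30; person SD 0.10; full adherence; two-sided alpha 0.05; no effect of mindfulness.

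**Step 1: SD of a person's mean change over 4 sessions.**
√(0.10² + 0.30²/4) = √(0.0100 + 0.0225) = 0.180.

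**Step 2: one-arm before-after test, n = 20.** Noncentrality = (r / 0.180) × √20, with 19 degrees of freedom and critical t of 2.09.

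| Rise r | r in SDs | Noncentrality | P(significant rise) |
|---|---|---|---|
| 0.05 | 0.277 | 1.24 | 22% |
| 0.10 | 0.555 | 2.48 | 65% |
| 0.15 | 0.832 | 3.72 | 94% |

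A simulation of 20,000 trials per scenario gave 21.9%, 65.9% and 94.2%. If all three app arms were counted (n = 60), still with no stimulation effect, the figures would be 56%, 99% and over 99%.

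**Step 3: mindfulness-only against control, 20 v 20.** Noncentrality = (difference in drift / 0.180) / √(2/20), with 38 degrees of freedom. The rise in the mindfulness arm is held at 0.10.

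| Drift during the puzzle | Difference in drift | Noncentrality | P(significant) |
|---|---|---|---|
| +0.10 (same as mindfulness) | 0 | 0 | 5% |
| 0 | 0.10 | 1.75 | 40% |
| −0.05 | 0.15 | 2.63 | 73% |

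The contrast removes drift that the arms share. It does not remove an effect of the puzzle itself.

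**Step 4: precision of the contrast.** In SDs of the person-level change, power with 20 v 20 is 15% at 0.3, 34% at 0.5 and 69% at 0.8; 80% needs about 0.91. On the assumed scale that is 0.91 × 0.180 = 0.16 log units. The half-width of the 95% interval is 2.02 × √(2/20) = 0.64 SD, or about 0.12 log units.

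**The case against.** H2.3 only predicts a direction. The comparative efficacy claims under Aim 2 are H2.1 and H2.2, both against control, so H2.3 can be read as a within-session check beside them. This stands in part: a reader might infer that the study will report any rise as an app effect, but no section says so. What the documents support is that the wording, placed under an efficacy aim, leaves that reading open.

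A reader might also infer that stimulated sessions will be pooled into Aim 2. The documents do not say that either. H2.1 and H2.2 concern mindfulness-only, and the combined intervention has its own Aims 3 and 4, so mindfulness-only is the natural reading of H2.3. The ambiguity is real, but one phrase settles it.

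The strongest objection concerns the remedy. It is tempting to say that comparing with control cuts false positives from about 65% to 5%. That holds only if HRV drifts equally in both tasks, and nothing in the documents supports equal drift between meditation and an online number puzzle. The second table under the working shows what happens otherwise. This stands: the contrast estimates mindfulness relative to the puzzle.

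Nor is the repair only a matter of wording. The strap is worn during sessions, and no before or after window is defined for either task. Without windows, neither the one-arm nor the two-arm version can be computed. This too stands, and it adds to the cost. None of these points is a reason to leave H2.3 without a comparator.

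**Conclusion.** The point holds in a limited form. As written, H2.3 cannot separate an app effect from non-specific change over a 10-minute evening session, and it does not say which arms count. The 22% to 94% range illustrates the exposure under assumed drift, SDs and full adherence; the lack of a comparator does not depend on those values. The control arm's scheduled strap recordings make a concurrent comparison possible. Mindfulness-only and control are the right pair: they are allocated by alternation within the same non-stimulation group, whereas the coordinator makes the split between stimulation and non-stimulation groups on practical grounds such as device availability (section 6.2). The contrast removes shared drift only, and with 20 per arm it yields an imprecise estimate. This is one secondary hypothesis in a pilot, so the change is worth making but does not threaten the study as a whole.

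**What to change.** - Restate H2.3 as the difference in within-session HRV change between mindfulness-only and control, and say that the stimulation arms are left out of it.
- Define the same early and late recording windows for the meditation session and the control task, and say that the hypothesis concerns recorded sessions, since the strap is not required in each one.
- Estimate the difference with a 95% confidence interval from a mixed model with sessions nested in participants. An interval suits an aim about preliminary effect sizes better than a test with 34% power at 0.5 SD.
- Report the mindfulness-only before-after change as descriptive, and state that the contrast is relative to the number puzzle, which may itself move HRV.

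**Cost.** A reworded hypothesis, one model and a short recording instruction for both arms. No new device or visit is needed. Matching windows may need some added procedure in the control arm: section 6.6 describes session and time data from the app account, but no logging is described for the puzzle, which is a web link. The price in inference is lower precision than a one-arm test.
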